Research Hypothesis We hypothesize that the anti-tumor effect of PD-L1/CTLA-4 blockade therapy is potentiated by the local ischemic treatment of transarterial chemo-embolization (DEB-TACE) in HCC by triggering a TH1 pro-inflammatory signal. We hypothesize that there are immediate changes in the tumor microenvironment and T cell diversity in serum after DEB-TACE. Thus, we hypothesize that the combined treatment with DEB-TACE followed by PD-L1/CTLA-4 blockade will synergistically enhance anti-tumor response in patients with HCC, and result in increased objective response rate (ORR).
Objectives: Primary Objectives: 
1. To evaluate the objective response rate (ORR) of patients with intermediate stage HCC treated with CTLA-4 (Tremelimumab) and PD-L1 (Durvalumab) with transarterial chemoembolization (DEB-TACE), according to modified response evaluation criteria in solid tumors (mRECIST). Secondary Objectives: 
1. To assess the safety of combining DEB-TACE with durvalumab and tremelimumab in patients with intermediate stage HCC Exploratory Objectives: 
1. To evaluate progression-free survival (PFS) and 6-month PFS of combining durvalumab and tremelimumab with DEB-TACE.2. To evaluate the tumor response of non-targeted lesion evaluated by objective response (mRECIST).3. To evaluate a 2 year overall survival (OS) of combining durvalumab and tremelimumab with DEB-TACE

4. To determine the effect of combined immune checkpoint and DEB-TACE versus DEB-TACE only on tumor microenvironment by comparing pre- and post-treatment tissue samples and peripheral blood tumor biomarkers including T cell receptor repertoire, circulating tumor cells, and circulating tumor DNA.
5. To explore potential molecular determinants of response, progression, and disease stability using next generation sequencing, other sequencing techniques, and other biomarkers.

Study Design:

This is an open-label, single institution study of combination treatment of tremelimumab and durvalumab with trans-arterial chemoembolization with drug-eluting microsphere beads (DEB-TACE) in patients with intermediate stage HCC. The purpose of this study is to determine the safety and efficacy of durvalumab and tremelimumab in this population who are receiving DEB-TACE as standard of care. Patients who have intermediate stage HCC according to Barcelona Clinic Liver Cancer (BCLC) criteria, who are eligible for locoregional treatment with DEB-TACE will be enrolled. 20 HCC patients will undergo DEB-TACE, followed by durvalumab 1500mg q4weeks and tremelimumab 300mg once within 2 weeks. Patients will continue with durvalumab q4weeks until progression of disease or the end of study or maximum 13 cycles. Patients will have radiographic surveillance every 6-8 weeks from their last DEB-TACE, and if there is residual tumor that can be targeted, patients will receive repeat DEB-TACE.

All patients will have pre- and post-TACE biopsies during the first DEB-TACE treatment and post-immunotherapy infusion biopsy.

Patients who are clinically stable at an initial confirmed progression may continue to receive study treatment, after the first overall time point assessment of PD until PD is confirmed on a follow-up scan (confirmed PD) if they do not show any significant toxicities. Patients will get a confirmatory scan, following the assessment of PD, at the next scheduled visit. Patients that continue on study after an initial PD will continue to receive durvalumab and tremelimumab at the same dose and schedule as they were treated with initially.

In addition, we will have 20 patient data for patients with HCC from our institutional database as exact matched control based on age, gender, tumor stage and Child-pugh score. We will evaluate the objective response rate (ORR) in comparison to the study group, using McNemar paired-sample test.

Number of Centers: 1

Study Population: 20

Patients with intermediate stage HCC, defined by the Barcelona Clinic Liver Cancer (BCLC) stage B with compensated cirrhosis who would be eligible for liver-directed therapy (e.g. DEB-TACE) as standard treatment.

Inclusion Criteria:

- Patients with diagnosis of HCC either by high-resolution imaging (triple-phase CT or MRI) and/or by tumor biopsy.

- Patient is not on systemic treatment for HCC. Prior local therapy with TACE is allowed if treatment was more than 1 month prior to enrollment with evidence of viable HCC or recurrence. Patients who were on tyrosine-kinase inhibitors (sorafenib, regorafenib, lenvatinib) or other systemic treatments for HCC but considered non-responders or intolerant to treatment are allowed to participate.
- Age ≥ 18
- ECOG performance status 0-1
- Body weight >30 kg
- HCC meeting Barcelona Clinic Liver Cancer (BCLC) stage B (intermediate stage), with measurable lesions on CT or MRI and without extrahepatic spread. Patients with BCLC stage A not considered candidates for transplant or surgery at the time of enrollment can participate if committed to remain on study for 6 months prior to consideration for alternative local therapies.
- Disease that is technically amenable to DEB-TACE. At least 1 radiographically measurable lesion that can be accurately measured at baseline as ≥ 10 mm in the longest diameter (except lymph nodes, which must have a short axis ≥ 15 mm) with CT or MRI.
- Patients with Child Pugh score of A or early B (score ≤ 8) without clinical evidence of ascites. Trace or small amounts of radiographic ascites without associated peritoneal carcinomatosis may be approved by the Protocol Chair.
- Adequate end-organ function as manifested by
 - a) Absolute neutrophil count of $\geq 1000/\text{mm}^3$
 - b) Hemoglobin $\geq 9.0 \text{ g/dL}$
 - c) platelets $\geq 75,000/\text{mm}^3$
 - d) Creatinine $\leq 2.0 \text{ mg/dL}$ or calculated creatinine clearance $> 50\text{mL/minute}$
 - e) AST ALT $\leq 5 \times \text{ULN}$ (pre-treatment value)
 - f) Total bilirubin: If cirrhosis present: Part of Child Pugh requirement.
If no cirrhosis present: total bilirubin $\leq 2 \text{ mg/dL}$
 - g) Albumin $\geq 2.5 \text{ g/dL}$
 - h) INR ≤ 1.8
- Negative urine or serum pregnancy test or evidence of post menopausal status (female patients only, post-menopausal status defined in protocol Section 4.1)
- Patient who is willing to get tumor biopsies per the study schedule.

Exclusion Criteria:

- Involvement in the planning and/or conduct of the study (applies to both AstraZeneca staff and/or staff at the study site).
- Participation in another clinical study with an last dose of investigational product ≤ 30 days prior to start of study treatment.
- Any concurrent anticancer therapy (chemotherapy, immunotherapy, endocrine therapy, targeted therapy, biologic therapy, tumour embolization, monoclonal antibodies) or receipt of the last dose ≤ 30 days prior to start of study treatment (TACE). Concurrent use of hormonal therapy for non-cancer-related conditions (e.g., hormone replacement therapy) is acceptable.
- Patients with vascular invasion or extrahepatic tumor.

- Main portal vein tumor-related thrombosis present on imaging. Non-tumor related thrombosis is allowed.
- Uncontrolled hepatic encephalopathy at the time of enrollement.
- Ascites that require ongoing paracentesis, within 4 weeks prior to the first scheduled dose, to control symptoms.
- Any contraindications for embolization, including hepatofugal blood flow or portosystemic shunt.
- Patients with detectable HBV viral load without active anti-viral treatment.
 - Patients with positive HepB surface antigen (HBsAg) and/or HepB core antibodies (anti-HBc) with detectable HBV DNA (≥ 10 IU/mL or above the limit of detection per local lab standard) are permitted on study if they are being treated with antiviral therapy with evidence of HBV stabilization or signs of viral response prior to enrollment. Patients who test positive for anti-HBc with undetectable HBV DNA (< 10 IU/ml or under the limit of detection per local lab standard) do not require anti-viral therapy prior to enrollment. (see Section 7.2.1 for additional on-study testing and anti-viral requirements)
- Any prior or concurrent malignancy or myeloproliferative disorder whose natural history or treatment has the potential to interfere with safety or efficacy assessment of this study's investigational drug.
- History of leptomeningeal carcinomatosis
- History of active primary immunodeficiency.
- Active infection including tuberculosis or human immunodeficiency virus.
- Any unresolved toxicity National Cancer Institute (NCI) Common Terminology Criteria for Adverse Event (CTCAE) Grade ≥ 2 from previous anticancer therapy with the exception of alopecia, vitiligo, and the laboratory values defined in the inclusion criteria:
 - Patients with Grade ≥ 2 neuropathy will be evaluated on a case-by-case basis after consultation with the Study Physician.
 - Patients with irreversible toxicity not reasonably expected to be exacerbated by treatment with durvalumab or tremelimumab may be included only after consultation with the Study Physician.
- Active or prior documented GI bleeding due to ulcer or esophageal varices bleeding within 6 months of enrollment. Note: For patients with history of esophageal variceal bleeding or assessed as high risk for esophageal variceal by the treating investigator, adequate endoscopic therapy according to institutional standards is required for assessment of esophageal varices. History of bleeding from other causes adequately treated are allowed.
- Major surgical procedure (as defined by the Investigator) within 28 days prior to the first dose of IP. Note: Local surgery of isolated lesions for palliative intent is acceptable.
- Current or prior use of immunosuppressive medication within 14 days before the first dose of durvalumab or tremelimumab. The following are exceptions to this criterion:
 - Intranasal, inhaled, topical steroids, or local steroid injections (e.g., intra articular injection)
 - Systemic corticosteroids at physiologic doses not to exceed 10 mg/day of prednisone or its equivalent
 - Steroids as a premedication for hypersensitivity reactions (e.g. CT scan premedication)

- Active or prior documented autoimmune or inflammatory disease (examples and exceptions listed in Section 4.1).
- Female patients who are pregnant or breastfeeding or male or female patients of reproductive potential who are not willing to employ effective birth control from screening to 90 days after last dose of durvalumab or 180 days after last dose of durvalumab + tremelimumab combination therapy
- Patients with hypothyroidism (e.g., following Hashimoto syndrome) who are not stable on hormone replacement.
- Any chronic skin condition that require systemic therapy.
- History of allogenic organ transplantation.
- History of pericarditis, cardiomyopathy or current use of defibrillator.
- Patients with celiac disease not controlled by diet alone.
- Uncontrolled intercurrent illness (see list of examples in Section 4.1)
- Receipt of live attenuated vaccine within 30 days prior to the first dose of IP. Note: Patients, if enrolled, should not receive live vaccine whilst receiving IP and up to 30 days after the last dose of IP.
- Known allergy or hypersensitivity to any of the study drugs or any of the study drug excipients.
- Prior randomisation or treatment in a previous durvalumab and/or tremelimumab clinical study regardless of treatment arm assignment.
- Patients who have received prior anti-PD-1, anti-PD-L1 or anti-CTLA-4 including durvalumab and tremelimumab.
- Judgment by the investigator that the patient is unsuitable to participate in the study and the patient is unlikely to comply with study procedures, restrictions and requirements.

Investigational Product(s), Dose, and Mode of Administration:

Durvalumab 1500mg Q4W plus tremelimumab 300mg once via IV infusion, starting at 2 weeks after first DEB-TACE procedure. This will be followed by durvalumab monotherapy 1500 mg via IV infusion Q4W, until progression or unacceptable toxicity (maximum 13 doses/cycles).

Study Assessments and Criteria for Evaluation:

Safety Assessments:

To ensure that the combination is safe, the first six patients will be treated and observed for toxicity for 1 cycle before continuation with further accrual. If ≤ 1 limiting toxicity events occur in the first 6 patients, we will proceed with additional accrual to complete a total of 20 patients for the safety evaluation. If > 1 limiting toxicity events occur among the first 6 patients, then three additional patients will be enrolled (i.e. a total of 9 patients). If ≤ 2 limiting toxicity events occur in the 9 patients, we will proceed with additional accrual to complete a total of 20 patients for the safety assessment. If > 2 limiting toxicity events occur, we will pause the enrollment pending safety review.

Efficacy Assessments:

The primary endpoint is objective response using modified RECIST (mRECIST) criteria. The regimen would be considered of insufficient activity for further study if the response rate is 30%

or less, and the minimum required level of efficacy that would warrant further study with the proposed regimen is a 60% response rate.

Statistical Methods and Data Analysis:

The safety evaluation will be based on the safety population, which includes all patients who receive DEB-TACE and at least one dose of either durvalumab or tremelimumab. Frequency of toxicity and adverse events will be summarized by type and grade. Primary efficacy analysis of best overall response will be based on response-evaluable population, which includes all patients who receive DEB-TACE and both durvalumab and tremelimumab, and have baseline scan and at least one on treatment scan or die without on treatment scan. Objective response rate, defined as the percent of patients who have CR or PR per mRECIST, will be estimated along with 95% confidence interval. Kaplan-Meier curves will be used to characterize progression-free survival (PFS) and overall survival. PFS rate at 6 month will be estimated from the Kaplan-Meier curve.

Objective response rate (ORR) from the exact matched control group (n=20) will be compared to the ORR of the study cohort using McNemar paired-sample test.

Sample Size Determination:

An optimal Simon two-stage design is planned. A total of 8 patients will be entered in the first stage. If ≤ 2 subjects respond, the treatment will be terminated and we will conclude the regimen is ineffective. If ≥ 3 subjects respond, then additional 12 patients will be studied. If a total of 8 or fewer subjects respond in stage one and two combined, the regimen is considered ineffective. If a total of 9 or more respond, we conclude the regimen is promising and warrants further study. The maximum sample size will be 20 evaluable patients. To account for 10% unevaluable patients who do not receive durvalumab/tremelimumab following DEB-TACE, or do not have any on treatment scans for reasons other than death, we plan to enroll 22 patients.

This design provides 90% power to detect a 30% absolute increase in ORR, from 30% to 60%, with one-sided type I error 0.1. The chance of stopping early for lack of efficacy at the interim analysis is 0.55, if the response rate is 30%.

STUDY SCHEMA

Figure 1: Schema

[figure not shown]

TABLE OF CONTENTS

PROTOCOL SYNOPSIS	3
STUDY SCHEMA.....	9
TABLE OF CONTENTS.....	10
LIST OF TABLES.....	13
LIST OF FIGURES	13
LIST OF APPENDICES.....	13
ABBREVIATIONS AND DEFINITION OF TERMS.....	14
1. INTRODUCTION	18
1.1 Disease background	18
1.1.1 Hepatocellular Carcinoma.....	18
1.1.2 Immunotherapies	18
1.1.3 Durvalumab	20
1.1.4 Tremelimumab	20
1.1.5 Durvalumab in combination with tremelimumab	20

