2.2 Secondary Objectives

- To assess the safety of combining DEB-TACE with durvalumab and tremelimumab in patients with intermediate stage HCC.

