3. STUDY DESIGN

This is an open-label, single institution, single arm study of combination treatment of durvalumab and tremelimumab in patients with intermediate stage HCC (BCLC B) undergoing trans-arterial chemoembolization.

Patients will be recruited from the Johns Hopkins Multidisciplinary Liver Cancer Clinic, general liver clinic, inpatient admissions with newly diagnosed HCC, and direct referrals to Interventional Radiology for DEB-TACE treatment. Once their diagnosis and staging is confirmed in Liver radiology tumor board as intermediate stage, patients will be screened for enrollment.

Enrolled patients will proceed with DEB-TACE procedure along with pre-treatment biopsy of tumor and surrounding non-tumor tissue. Following their DEB-TACE procedure, patients will be followed in 7-10 days in hepatology clinic with labs for any new decompensating signs or symptoms. If the patient does not have any ongoing new decompensation, they will proceed with a 2nd biopsy, followed by 1st infusion of durvalumab 1500mg and tremelimumab 300mg 2 weeks after DEB-TACE. This will be followed by durvalumab 1500mg q4weeks until progression of disease, the end of study, or maximum 13 cycles.

All patients will receive repeat DEB-TACE every 8 weeks if there is residual tumor that can be targeted. A third biopsy will be done after 2 doses of durvalumab infusion during their second DEB-TACE procedure at week 8, unless the patient has CR.

Patients will have an MRI (or CT if contraindicated) at Week 6 and Week 14, then every 3 months unless additional DEB-TACE is needed. Patients who are clinically stable at initial disease progression may continue to receive study treatment until PD is confirmed on a follow-up scan (confirmed PD) if they do not show any significant toxicities. Patients will get a confirmatory scan, following the assessment of PD, at the next scheduled visit. Patients will continue to receive durvalumab and tremelimumab with the same dose and schedule as they were treated with initially.

Additionally, 20 patients from the institutional database will be selected as exact matched control based on age, gender, tumor stage and Child-Pugh score. We will evaluate the objective response rate (ORR) in comparison to the study group, using McNamer paired-sample test.

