4.4 Replacement of patients

If a patient is lost to follow up after the first DEB-TACE or deemed not appropriate for further treatment with durvalumab or tremelimumab due to medical complications, patients will be replaced. If patients do not have treatment scans for reasons other than death, patients will be replaced.

[figure not shown]
[figure not shown]
[figure not shown]

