11. STATISTICAL METHODS AND SAMPLE SIZE DETERMINATION

11.1 Description of analysis sets

11.1.1 Safety analysis set

Safety analysis set includes all patients who receive any study treatment including DEB-TACE or at least one dose of either durvalumab or tremelimumab.

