11.2 Methods of statistical analyses

11.2.1 Safety analyses

Safety will be summarized by the percentage of patients with AEs, by type and grade according to NCI CTCAE version 5.0 and attribution. The analysis will be based on safety analysis set.

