11.2.2 Efficacy analyses

The primary endpoint is objective response. Objective response rate, defined as the percent of patients with at least one visit response of CR or PR via mRECIST and will be based on the Evaluable Population.

As a secondary endpoint, the response of non-target lesions will be described. Other secondary efficacy endpoints include duration of response, 6-month progression-free survival, and overall survival (OS). Duration of response is defined as date of having CR or PR to the date of progression per mRECIST among the patients who have CR or PR. Progression free survival will be defined as the time from the date of start of the treatment until the documentation of disease progression according to mRECIST or death due to any cause, whichever occurs first. Patients who have not progressed or died at the time of the analysis will be censored at the time of the latest date of assessment from their last evaluable mRECIST assessment. Kaplan-Meier

curves will be used to characterize PFS and OS, and 6-month PFS will be estimated from Kaplan-Meier.

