11.3 Determination of sample size

The standard of care treatment with DEB-TACE results in a objective response rate (ORR) of 30%. The regimen would be considered of insufficient activity for further study if the ORR is 30% or less, and the minimum required level of efficacy that would warrant further study with the proposed regimen is a 60% response rate. An optimal Simon two-stage design is planned. A total of 8 patients will be entered in the first stage. If ≤ 2 subjects respond, the treatment will be terminated and we will conclude the regimen is ineffective. If ≥ 3 subjects respond, then additional 12 patients will be studied. If a total of 8 or fewer subjects respond in stage one and two combined, the regimen is considered ineffective. If a total of 9 or more respond, we conclude the regimen is promising and warrants further study. The maximum sample size will be 20 evaluable patients. To account for 10% unevaluable patients who do not receive durvalumab/tremelimumab following DEB-TACE, or do not have any on treatment scans for reasons other than death, we plan to enroll 22 patients.

This design provides 90% power to detect a 30% absolute increase in ORR, from 30% to 60%, with one-sided type I error 0.1. The chance of stopping early for lack of efficacy at the interim analysis is 0.55, if the response rate is 30%.

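### The synopsis and Section 11.1.1 define the safety population differently, and the synopsis version leaves patients who had DEB-TACE but never started immunotherapy out of the adverse event summary

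*Combined protocol and SAP*

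**What the plan says.** The synopsis, under Statistical Methods and Data Analysis, bases the safety evaluation on a population "which includes all patients who receive DEB-TACE and at least one dose of either durvalumab or tremelimumab".

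Section 11.1.1 reads: "Safety analysis set includes all patients who receive any study treatment including DEB-TACE or at least one dose of either durvalumab or tremelimumab". Section 11.2.1 then says of the adverse event summary: "The analysis will be based on safety analysis set".

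Three other places show that patients may have DEB-TACE and go no further:

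- Section 3 puts a check between DEB-TACE and the first infusion, at a clinic visit 7 to 10 days after the procedure: "If the patient does not have any ongoing new decompensation, they will proceed with a 2nd biopsy", with the infusion after that.
- Section 4.4 says that if a patient is lost after the first DEB-TACE, or is "deemed not appropriate for further treatment with durvalumab or tremelimumab due to medical complications, patients will be replaced".
- Section 11.3 (and the synopsis) explains why 22 patients are enrolled for 20 evaluable: "To account for 10% unevaluable patients who do not receive durvalumab/tremelimumab following DEB-TACE", or who lack an on-treatment scan for a reason other than death.

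Section 2.2 lists one secondary objective: "To assess the safety of combining DEB-TACE with durvalumab and tremelimumab in patients with intermediate stage HCC".

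**The concern.** One definition joins the two components with *and*, the other with *or*. DEB-TACE comes first, so the patients who separate the two sets are in practice those who had the procedure and never received either drug. The *or* would also admit someone given drug without DEB-TACE, but the treatment sequence makes that unlikely.

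Membership of this group can depend on outcome. A patient who decompensates after DEB-TACE may be held back from the infusion for that reason. Under the synopsis definition the patient then leaves both numerator and denominator, and the reported rates become conditional on having come through the first step well enough to start the second. The response-evaluable set in Section 11.1.2 requires both drugs, so under the synopsis wording these patients belong to no defined analysis set.

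At stake is the descriptive adverse event summary for the only secondary objective. As the text stands, an analyst could follow either definition and cite the protocol for it.

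**Working it through.** **The plan's own figures.** Enrolment: 20 × 1.10 = 22, as stated. (Dividing instead, 20/0.90 = 22.2, gives 23. The difference does not matter here.) The two-stage design (8 then 12 patients, stop at 2 or fewer responses, ineffective at 8 or fewer of 20) also reproduces by exact binomial calculation: early stopping 0.552 at a 30% response rate (stated 0.55), type I error 0.0999 (stated 0.1), and power 0.912 at 60% (stated 90%). These use the response-evaluable set, so neither safety definition enters them.

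**The definitions side by side.**

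| Patient received | Synopsis | Section 11.1.1 |
|---|---|---|
| DEB-TACE and at least one drug dose | in | in |
| DEB-TACE only | out | in |

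**Inputs for sizing the gap.** Treated patients: 22, the planned enrolment in Section 11.3. Let d be the number with DEB-TACE only. The documents give no figure for d. I take 0 to 2, because the 10% allowance is 2 patients (22 − 20) and also covers patients without scans, who stay in both sets if they were dosed. Section 4.4 puts no cap on replacements, so 2 is a planning value and not a limit.

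**Formula.** Let e be the number of drug recipients with a given event, and suppose all d DEB-TACE-only patients have it. The synopsis rate is e/(22 − d). The Section 11.1.1 rate is (e + d)/22.

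| d | e | Synopsis | Section 11.1.1 |
|---|---|---|---|
| 0 | 0 | 0/22 = 0% | 0/22 = 0% |
| 1 | 0 | 0/21 = 0% | 1/22 = 4.5% |
| 2 | 0 | 0/20 = 0% | 2/22 = 9.1% |
| 2 | 2 | 2/20 = 10.0% | 4/22 = 18.2% |

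Exact (Clopper-Pearson) 95% intervals for d = 2, e = 0: for 0/20 the upper limit is 1 − 0.025^(1/20) = 16.8%, giving 0 to 16.8%. For 2/22 the beta quantiles give 1.1 to 29.2%.

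**The effect in the other direction.** For an event that only the drugs can cause, adding patients who were never dosed lowers the rate. With 4 such events and d = 2, 4/20 = 20.0% becomes 4/22 = 18.2%.

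**Does any decision use the safety set?** The run-in in Section 11.2.4 counts limiting toxicities, which Section 6.3 assesses from the first administration of either drug. The go/no-go rule in Section 11.3 uses evaluable patients. Section 11.2.1 reports percentages, with no test or threshold. No rule depends on which definition is used.

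**The case against.** The strongest reply is that the statistical section is already right. Section 11.1.1 gives the inclusive set and Section 11.2.1 applies it, so what remains is one synopsis sentence out of step. That largely stands, and it shows which way to correct the text. It does not remove the conflict, because the synopsis sentence is explicit and no rule of precedence is given.

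A second reply is that DEB-TACE is standard of care here and the stated purpose is to study the two drugs in patients receiving it, so a set that received both components is a fair denominator for the combination. This stands in part: the dilution of drug-related rates is real, and is a reason to show the dosed subset as well. But Section 11.1.1 itself counts DEB-TACE as study treatment, the exclusion on concurrent anticancer therapy treats TACE as the start of study treatment, and these patients also undergo a protocol biopsy with the procedure. Failing to reach the second step is part of the safety of the sequence.

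A reader might infer that the plan conceals harm after DEB-TACE. The documents do not support that. Adverse events are recorded from consent (Section 10.3.1). Serious events are assessed for relation to protocol procedures even before any drug is given (Section 10.3.3), go to the IND sponsor and the drug company within 24 hours (Section 10.3.11), and are reported to the IRB (Section 10.3.11.2). The omission would be from the summary table.

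A reader might also infer that everyone excluded had an adverse outcome. Section 4.4 also covers loss to follow-up, which need not be one.

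**Conclusion.** The two definitions conflict, and nothing in the documents reconciles them. Followed as written, the synopsis version would drop DEB-TACE-only patients from the adverse event summary, and for some of them the reason for dropping out would be the event itself.

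The size is modest. With 22 treated patients and 0 to 2 of them DEB-TACE-only, the gap runs from nothing (d = 0, where the sets coincide) to 0% against 9.1%. The upper end is close to a worst case. It needs the whole 10% allowance to be DEB-TACE-only, both of those patients to have the event, and no drug recipient to have it. The intervals at that end overlap heavily (0 to 16.8% and 1.1 to 29.2%).

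Safety is the only secondary *objective*. It would be tempting to call it the only secondary *endpoint*, but Section 11.2.2 also labels non-target lesion response, duration of response, 6-month progression-free survival and overall survival as secondary. Nor does the conflict reach the run-in rule, the Simon design or the sample size. It is a consistency error with a possible outcome-dependent effect on a descriptive table, and worth correcting for that reason.

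**What to change.** Reword the synopsis sentence so that the safety population matches Section 11.1.1: every patient who receives any study treatment, including DEB-TACE alone. Base the main adverse event table on that set, as Section 11.2.1 already directs. Beside it, show the subset who received at least one dose of durvalumab or tremelimumab, under its own name, so that drug-related rates can be read without dilution.

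The cost is one sentence in the synopsis and one extra table column. It needs no new data, no additional patients and no change to the design or to any treatment rule.
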